2.2 Study Design Overview

The schematic of the study is shown in [Figure 1](#).

Figure 1. Study Schematic

RZB- Risankizumab
APR- Apremilast; *dose titration Day 1 to Day 5
**Stratified by PASI 75 Response Status (Yes/No)

↓ Rescue with RZB for APR arm allowed for subjects < PASI 50 starting at Week 28 OR Week 40

BID = twice daily; PASI = Psoriasis Area Severity Index; SC = subcutaneous

2.3 Treatment Assignment and Blinding

All subjects will be assigned a unique identification number by the IRT at the screening visit. For subjects who rescreen, the screening number assigned by the IRT at the initial screening visit should be used. The IRT will assign a randomization number that will encode the subject's treatment group assignment according to the randomization schedule.

In Period A (Baseline to Week 16), subjects will be centrally randomized to risankizumab (Arm 1) or apremilast (Arm 2) in a 1:2 ratio at Baseline. Randomization will be stratified

by Baseline body weight (≤ 100 kg, > 100 kg) and prior exposure to any systemic and/or biologic treatment for Po ($0, \geq 1$).

In Period B (Week 16 to Week 52), subjects initially randomized to risankizumab (Arm 1) will continue to receive risankizumab. Subjects initially randomized to apremilast (Arm 2) will be centrally re-randomized at the Week 16 visit in a 1:1 ratio to receive either risankizumab (Arm 2a) or apremilast (Arm 2b). Re-randomization will be stratified by PASI 75 response (responder, non-responder) at Week 16. Rescue risankizumab will be offered to subjects who are re-randomized to apremilast (Arm 2b) and are PASI 50 non-responders at Week 28 (Arm 3a) or Week 40 (Arm 3b).

This is an open-label study; however, the efficacy assessor will remain blinded to each subject's treatment, clinical laboratory results, and all subject safety data during the course of the study.

2.4 Sample Size Determination

This study plans to enroll a total of $N = 330$ subjects, to be sufficiently powered to detect the treatment difference between risankizumab (RZB) and apremilast (APR) with respect to the co-primary endpoints in Period A, as well as between APR/RZB and APR/APR with respect to the primary endpoint in Period B:

- Assuming that 50% of APR-PASI75NR subjects in the APR/RZB group and 20% of APR-PASI75NR subjects in the APR/APR group will achieve PASI 90 at Week 52 in Period B, the sample size of 120 re-randomized APR-PASI75NR subjects (60 subjects per group) will have more than 90% power to detect the treatment difference between APR/RZB and APR/APR, using a Chi-square test with a 2-sided significance level of 0.05.
- Assuming 55% of subjects initially randomized to APR will be re-randomized at Week 16 under the APR-PASI75NR (as defined by the PASI 75 response at Week 16) stratum, the total sample size for the initial APR group is $120/55\% = 220$. Assuming the treatment difference is at least 40% with respect to the co-primary endpoints of PASI 90 and sPGA of 0 or 1 at Week 16 in Period A, the total sample size of $N = 330$ subjects (RZB: 110, APR: 220) will

also provide more than 90% power to detect the treatment difference between RZB and APR, using a Chi-square test with a 2-sided significance level of 0.05.

3.0 Endpoints

3.1 Primary Endpoints

The co-primary endpoints of this study in Period A are:

- Achievement of PASI 90 at Week 16, among subjects in the ITT_A Population.
- Achievement of sPGA 0 or 1 with at least 2-grade improvement from Baseline at Week 16, among subjects in the ITT_A Population.

The primary endpoint of this study in Period B is:

- Achievement of PASI 90 at Week 52, among subjects in the ITT_B_NR Population.

3.2 Secondary Endpoints

The ranked and only secondary endpoint of this study in Period A is:

1. Achievement of PASI 75 at Week 16, among subjects in the ITT_A Population.

The ranked secondary endpoints of this study in Period B are:

1. Achievement of PASI 75 at Week 52, among subjects in the ITT_B_NR Population.
2. Achievement of sPGA 0 or 1 with at least 2-grade improvement from Baseline at Week 52, among subjects in the ITT_B_NR Population.

3.3 Other Efficacy Endpoints

All variables listed in Section 3.1 and Section 3.2 as primary or ranked secondary endpoints will also be analyzed at all other visits collected. Additionally, the following endpoints will be evaluated at all visits collected:

- Achievement of 100% reduction from Baseline in PASI (PASI 100)
- Achievement of sPGA 0
- Change from Baseline in PASI
- Percent change from Baseline in PASI
- Change from Baseline in body surface area (BSA)
- Achievement of Palmoplantar Investigator's Global Assessment (ppIGA) 0 or 1, among subjects with Baseline ppIGA of at least 3
- Change from Baseline in Psoriasis Scalp Severity Index (PSSI), among subjects with Baseline scores > 0
- Change from Baseline in Nail Psoriasis Severity Index (NAPSI), among subjects with Baseline scores > 0
- Change from Baseline in Dermatology Life Quality Index (DLQI)
- Achievement of DLQI 0 or 1
- Achievement of DLQI improvement (reduction) of ≥ 4 points, among subjects with Baseline DLQI ≥ 4
- Change from Baseline in Work Productivity and Activity Impairment (WPAI) scores
- Treatment Satisfaction Questionnaire for Medication version 9 (TSQM-9) scores (at each post-Baseline visit in Period A)
- Change from Entry of Period B in TSQM-9 scores, among subjects who are re-randomized at Week 16
- Change from Baseline in Psoriasis Symptoms Scale (PSS) scores
- Percentage change from Baseline in PSS, among subjects with baseline scores > 0
- Achievement of PSS 0

- Achievement of PSS 0 or 1

3.4 Safety Endpoints

The following safety evaluations will be performed throughout the study as measures of safety and tolerability:

- Adverse event (AE) monitoring
- Vital sign measurements
- Physical examinations
- Clinical laboratory testing (hematology and chemistry)

3.5 Additional Endpoints

Not applicable.

4.0 Analysis Populations

The following analysis populations will be used for the analyses.

The Intent to Treat Population in Period A (ITT_A) includes all randomized subjects. The ITT_A Population will be used for all efficacy analyses in Period A.

The Intent to Treat Population for APR-PASI75NRs in Period B (ITT_B_NR) includes subjects randomized at Baseline (Day 1), fail to achieve PASI 75 at Week 16 and are re-randomized. The ITT_B_NR Population will be used for the analysis comparing switch-to-RZB (APR/RZB) vs. continue-with-APR (APR/APR) among APR-PASI75NRs in Period B.

The Intent to Treat Population for APR-PASI75 responders in Period B (ITT_B_R) includes subjects randomized to APR at baseline, achieve PASI 75 at Week 16 and are re-randomized (APR-PASI75Rs). The ITT_B_R Population will be used for the summary of efficacy for APR/RZB and APR/APR among APR-PASI75Rs in Period B.

The Intent to Treat Population for Period B combined Population (ITT_B_Combined) includes subjects randomized to APR at Baseline and are re-randomized at Week 16. The ITT_B_Combined Population will be used for combined analysis (APR-PASI75NRs and APR-PASI75Rs) between subjects re-randomized to APR/RZB and APR/APR in Period B.

The Intent to Treat Population for Long Term Efficacy (ITT_LT) includes subjects randomized to receive continuous RZB (i.e., all subjects randomized to RZB at Baseline) and subjects randomized and re-randomized to receive continuous APR, including half of the subjects randomized to APR at Baseline and prematurely discontinued from study before entering Period B. The ITT_LT Population will be used for the analysis comparing long term efficacy between continuous treatment of RZB/RZB and APR/APR in Period B. Of note, the algorithm to select half of the subjects randomized to APR at Baseline and prematurely discontinued from study before entering Period B is defined as follow:

1. Rank all such subjects by their subject ID in ascending order (as 1, 2, 3...).
2. Select subjects whose ranks are even numbers.

The Intent to Treat Population for Rescued Population (ITT_Res) includes subjects who are re-randomized to APR at Week 16, fail to achieve PASI 50 at Week 28 and/or Week 40, and receive RZB as the rescue medication. The ITT_Res Population will be used for the summary of efficacy after being rescued with RZB.

Each ITT Population will have a corresponding Safety Population, consists of subjects who received at least one dose of study drug during the specific Study Period. In addition, an all risankizumab treated (ALL_RZB) Population will be utilized for a comprehensive safety summary of RZB. The ALL_RZB Population is defined as all subjects who receive at least one dose of RZB as the study drug.

5.0 Subject Disposition

A summary of subject disposition in Period A will be provided among the ITT_A Population, where the number of subjects in each of the following categories will be summarized for each treatment group:

- Subjects randomized in the study;
- Subjects who took at least one dose of study drug in Period A;
- Subjects who completed protocol-specified treatment in Period A;
- Subjects who prematurely discontinued study drug in Period A (by reasons);
- Subjects who completed Period A

Summaries of subject disposition in Period B will be provided among the ITT_B_R and the ITT_B_NR Populations, as well as the RZB group in the ITT_LT Population, where the number of subjects in each of the following categories will be summarized for each treatment group:

- Subjects re-randomized in Period B (or Subjects who entered Period B among the ITT_LT Population);
- Subjects who took at least one dose of study drug in Period B;
- Subjects who received RZB as the rescue medication (not applicable to the ITT_LT Population);
- Subjects who completed protocol-specified treatment in Period B;
- Subjects who prematurely discontinued study drug in Period B (by reasons);
- Subjects who completed the study.

For end of study participation, the number and percentage of subjects who did not complete each Study Period with associated reasons will be summarized overall and by treatment group.

6.0 Study Drug Duration and Compliance

Duration of treatment will be summarized by treatment groups among the Safety_A, Safety_B_R, Safety_B_NR, and Safety_Res Populations as well as the RZB group in the Safety_LT Population. In addition, duration of any RZB will be summarized among the ALL_RZB Population.

The duration of RZB for each period is defined as follows:

Period A: the minimum of (the last dose date in Period A + 84 days, the end of study date + 1 day, and the first dose date in Period B if not missing [and cutoff date during the Primary Analysis for Period A + 1 day]) minus the first dose date in Period A.

Period B: the minimum of (the last dose date in Period B + 84 days, and the end of study date + 1 day [and cutoff date during the Primary Analysis for Period B + 1 day]) minus the first dose date in Period B.

Rescue RZB: the minimum of (the last dose date of rescue risankizumab + 84 days, the end of study date + 1 day [and cutoff date during the Primary Analysis for Period B + 1 day]) minus the first dose date of rescue risankizumab.

ALL_RZB: the minimum of (the last dose date of risankizumab + 84 days, and the end of study date + 1 day [and cutoff date during the Primary Analysis for Period B + 1 day]) minus the first dose date of risankizumab.

The duration of APR for each period is defined as follows:

Period A: the minimum of (the last dose date in Period A + 1 day, the end of study date + 1 day, and the first dose date in Period B if not missing [and cutoff date during the Primary Analysis for Period A + 1 day]) minus the first dose date in Period A.

Period B: the minimum of (the last dose date in Period B + 1 day, the start date of rescue RZB if applicable, and the end of study date + 1 day [and cutoff date during the Primary Analysis for Period B + 1 day]) minus the first dose date in Period B.

Duration of treatment will be summarized by descriptive statistics of mean, standard deviation, median, minimum and maximum, among the number of subjects treated in each period.

Treatment compliance will be summarized by treatment groups among the Safety_A, Safety_B_R, Safety_B_NR, and Safety_Res Populations as well as the RZB group in the Safety_LT Population.

The compliance for RZB will be summarized by the percentage of planned injections which are administered in each analysis period. The compliance for APR will be summarized by the number of APR tablets actually taken (i.e., the difference between the number of tablets dispensed and the number of tablets returned) by the subject divided by the number of tablets planned to be taken by the subject in each analysis period. When computing the compliance for each treatment group, the denominator will include all subjects in this treatment group who received at least one dose of study drug in the Study Period. For subjects who prematurely discontinued the study drug, the planned injections/tablets will only be counted prior to that scheduled visit of discontinuation. For subjects who are rescued, the planned APR tablets will only be counted prior to the first dose date of rescue RZB.

7.0 Demographics, Baseline Characteristics, Medical History, and Prior/Concomitant Medications

7.1 Demographics and Baseline Characteristics

Continuous demographic variables include age, weight, height, and body mass index (BMI). Categorical demographic variables include sex, ethnicity, race, age (< 40 or ≥ 40 years), weight (≤ 100 or > 100 kg), BMI (< 25, ≥ 25 – < 30, ≥ 30 kg/m²), tobacco user (current, former, never, unknown), and alcohol user (current, former, never, unknown).

Baseline disease characteristics include history of psoriatic arthritis (yes, no), Baseline ppIGA categories, Baseline sPGA categories, Baseline PASI, Baseline NAPSI, Baseline PSSI, Baseline BSA, Baseline WPAI, Baseline PSS and Baseline DLQI.

Demographics and baseline disease characteristics will be summarized among the ITT_A, ITT_B_R, ITT_B_NR, and ITT_Res Populations, overall and by treatment groups. Categorical variables will be summarized with the number and percentage of subjects; percentages will be calculated based on the number of non-missing observations. Continuous variables will be summarized with descriptive statistics (number of non-missing observations, mean, standard deviation, median, minimum and maximum).

7.2 Medical History

Medical history data will be coded using the Medical Dictionary for Regulatory Activities (MedDRA). The actual version of the MedDRA coding dictionary will be noted in the statistical tables and clinical study report. The number and percentage of subjects in each medical history category (by MedDRA system organ class and preferred term) will be summarized overall and by treatment group. The system organ class (SOC) will be presented in alphabetical order, and the preferred terms will be presented in alphabetical order within each SOC. Subjects reporting more than one condition/diagnosis will be counted only once in each row (SOC or preferred term).

Medical history will be summarized among the ITT_A, ITT_B_R, and ITT_B_NR Populations.

7.3 Prior and Concomitant Medications

Prior and concomitant medications will be summarized by generic name. A prior medication is defined as any medication taken prior to the date of the first dose of study drug. A concomitant medication is defined as any medication that started prior to the date of the first dose of study drug and continued to be taken after the first dose of study drug or any medication that started on or after the date of the first dose of study drug, but not after the minimum of {the date of the last dose of RZB plus 140 days, the date of the last

dose of APR plus 28 days}. The number and percentage of subjects taking medications will be summarized by generic drug name based on the World Health Organization (WHO) Drug Dictionary for both prior and concomitant medications.

In addition, subjects' prior biologic therapy for psoriasis will also be summarized by the reason for discontinuation.

Prior and concomitant medications will be summarized among the ITT_A, ITT_B_R, and ITT_B_NR Population as well as the RZB group in the ITT_LT Population.

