## 4 INVESTIGATIONAL PLAN

### 4.1 Overall Study Design and Plan

---

This is a Phase 4, global, multicenter, randomized, open-label, efficacy assessor-blinded, active comparator study examining the effect of risankizumab compared to apremilast in adult subjects with moderate plaque PsO who are candidates for systemic therapy.

The study is designed to enroll 330 subjects. See Section 5.1 for information regarding enrollment criteria.

The study duration for subjects administered risankizumab or provided apremilast will be up to approximately 69 weeks or 61 weeks, respectively. The study is comprised of a Screening period of up to 35 days, a 52week treatment period, and a follow-up phone call for safety. Depending on the

[figure not shown]
treatment at the end of the study, the follow-up phone call for safety will be conducted approximately 20 weeks (140 days) after administration of the last dose of risankizumab (i.e., Week 40 for subjects originally randomized to risankizumab and Week 44 for subjects switched from apremilast to risankizumab) or approximately 4 weeks (28 days) after the last dose of apremilast (for subjects who remain on the APR arm after re-randomization).

The 52-week treatment duration includes Period A and Period B:

- Period A (Baseline to Week 16): Eligible subjects will be centrally randomized at the Baseline (Day 1) visit in a 1:2 ratio to receive either risankizumab 150 mg as a single subcutaneous (SC) injection (Arm 1) or apremilast 30 mg orally twice daily (BID) (Arm 2). The randomization will be stratified by Baseline body weight ( $\leq 100$  kg,  $> 100$  kg) and prior exposure to any systemic and/or biologic treatment for PsO (0,  $\geq 1$ ). Study drug administration for apremilast will occur beginning at Baseline (Day 1) based on the dose titration schedule from Day 1 to Day 5 and will continue with 30 mg BID until the day prior to the Week 16 visit where re-randomization will occur. Study drug administration for risankizumab will occur at Baseline (Day 1) and Week 4. The final efficacy evaluation for Period A will take place at Week 16.

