- Period B (Week 16 to Week 52): Subjects initially randomized to risankizumab (Arm 1) will continue to receive risankizumab 150 mg as a single SC injection at Weeks 16, 28, and 40. Subjects initially randomized to apremilast (Arm 2) will be re-randomized at the Week 16 visit in a 1:1 ratio to receive either risankizumab 150 mg as a single SC injection at Weeks 16, 20, 32, and 44 (Arm 2a) or apremilast 30 mg orally BID up to Week 52 (Arm 2b). Rerandomization will be stratified by PASI 75 response (responder, non-responder) at Week 16. Rescue risankizumab will be offered to subjects who are re-randomized to apremilast (Arm 2b) and are PASI 50 non-responders at Week 28 (Arm 3a; rescue risankizumab will be administered at Weeks 28, 32, and 44) or Week 40 (Arm 3b; rescue risankizumab will be administered at Weeks 40 and 44). The final efficacy evaluation will take place at Week 52.

The schematic of the study is shown in [Figure 1](#). Further details regarding study procedures are located in the Operations Manual ([Appendix F](#)).

Figure 1. Study Schematic

RZB- Risankizumab  
 APR- Apremilast; \*dose titration Day 1 to Day 5  
 \*\*Stratified by PASI 75 Response Status (Yes/No)

↓ Rescue with RZB for APR arm will be offered to subjects < PASI 50 starting at Week 28 **OR** Week 40

BID = twice daily; PASI = Psoriasis Area Severity Index; SC = subcutaneous

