## 5.4 Prior and Concomitant Therapy

---

Stable doses of other concomitant therapies for chronic conditions, for which neither the condition nor the treatment are judged to exclude the subject from participation, are permissible. All concomitant medications should be carefully evaluated by the investigator.

Any medication or vaccine (including over-the-counter or prescription medicines, vitamins, and/or herbal supplements) that the subject has received from 4 weeks prior to Screening or receives during the study must be recorded along with the reason for use; date(s) of administration, including start and end dates; and dosage information including dose, route, and frequency on the appropriate electronic case report form (eCRF).

A detailed history of all prior biologic use will be obtained in the electronic data capture (EDC).

Any questions regarding concomitant or prior therapy should be raised to the AbbVie emergency contact. Information regarding potential drug interactions with risankizumab and/or apremilast can be located in the risankizumab Investigator's Brochure or apremilast label.

Subjects must be able to safely discontinue any prohibited medications (including biologics) 5 half-lives or 4 weeks, whichever is longer, prior to initial study drug administration. Subjects must be consented for the study prior to discontinuing any prohibited medications for the purpose of meeting study eligibility.

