### Study Activities Table

| Activity  | Screening            | Baseline | Week 4 | Week 16 | Week 20 | Week 28 | Week 32 | Week 40 | Week 44 | Week 52
Premature
Discontinuation | Safety Follow-up Call |
|---|----------------------|----------|--------|---------|---------|---------|---------|---------|---------|---|-----------------------|
|   | Day -35 to
Day -1 | Day 1    | Day 29 | Day 113 | Day 141 | Day 197 | Day 225 | Day 281 | Day 309 | Day 365                                 |                       |
| Visit Window  | ± 3 Days             |          |        |         |         |         |         |         |         |   |                       |
| INTERVIEWS & QUESTIONNAIRES  |                      |          |        |         |         |         |         |         |         |   |                       |
| Informed consent  | ✓                    |          |        |         |         |         |         |         |         |   |                       |
| Eligibility criteria  | ✓                    | ✓        |        |         |         |         |         |         |         |   |                       |
| Medical (including psoriasis)/surgical history  | ✓                    | ✓        |        |         |         |         |         |         |         |   |                       |
| Demographics  | ✓                    |          |        |         |         |         |         |         |         |   |                       |
| Alcohol, nicotine, and e-cigarette use  | ✓                    |          |        |         |         |         |         |         |         |   |                       |
| Token information (US only)   | ✓                    |          |        |         |         |         |         |         |         |   |                       |
| Adverse event assessment  | ✓                    | ✓        | ✓      | ✓       | ✓       | ✓       | ✓       | ✓       | ✓       | ✓                                       | ✓                     |
| Prior/concomitant therapy   | ✓                    | ✓        | ✓      | ✓       | ✓       | ✓       | ✓       | ✓       | ✓       | ✓                                       | ✓                     |

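### Two descriptive time windows in the SAP are wrong as written: Section 7.3 stops counting new medications at about Day 140 in switched subjects, and the ALL_RZB line of Section 10.2.4 names the Period A cutoff

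*SAP*

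**What the plan says.** **Medications.** Under SAP 7.3, medications started before the first dose and continued are concomitant. So are new starts, described as "any medication that started on or after the date of the first dose of study drug". An upper limit applies to these new starts: they count "but not after the minimum of {the date of the last dose of RZB plus 140 days, the date of the last", where the second date in the braces is 28 days past the final apremilast intake. One definition serves every table. The tables "will be summarized among the ITT_A, ITT_B_R, and ITT_B_NR Population as well as the RZB group in the ITT_LT Population". Collection is wider than this window. Protocol 5.4 requires that any medication the subject "receives during the study must be recorded along with the reason for use", and the Protocol Appendix D row "Prior/concomitant therapy" is ticked at every visit and at the safety follow-up call.

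The design puts many subjects on both drugs. In Period A apremilast "will continue with 30 mg BID until the day prior to the Week 16 visit where re-randomization will occur" (Protocol 4.1). Half of those re-randomized then receive risankizumab "150 mg as a single SC injection at Weeks 16, 20, 32, and 44 (Arm 2a"), and apremilast continuers who are rescued also move to risankizumab.

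**ALL_RZB patient-years.** SAP 10.2.4 ends exposure at the earliest of several dates, with a bracketed data cutoff added. For the RZB/RZB, APR/RZB, APR/APR and rescue lines the bracket names the Primary Analysis for Period B. For ALL_RZB it names the Primary Analysis for Period A. SAP 6.0 defines ALL_RZB treatment duration with the Period B cutoff.

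**The concern.** A minimum of two drug-specific dates does no harm in a subject who takes one drug. In a subject who takes both in sequence it always selects the date of the drug stopped first. Medications started while the second drug is being given then drop out of the table although they were collected, and this happens mainly in one of the two re-randomized arms. In the ITT_B_NR and ITT_B_R tables a lower count of new starts under APR/RZB could simply reflect a shorter window.

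For ALL_RZB the stake is the denominator of events per 100 patient-years in the pooled risankizumab summary. Most of that exposure is also counted in lines that carry the Period B cutoff, so two parts of one table set could be truncated differently at the same analysis.

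**Working it through.** **1. SAP 7.3 window**

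Inputs: the visit days in Protocol Appendix D follow day = 7 × week + 1. Week 16 = 113, Week 28 = 197, Week 40 = 281, Week 44 = 309 and Week 52 = 365 all reproduce. The last apremilast dose before a switch is the day before Week 16, Day 112. Apremilast is assumed to stop the day before the first rescue dose (Day 196 or 280). Continuers take apremilast up to Week 52, taken here as Day 365.

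Window end = min(last RZB + 140, last APR + 28), using the dates that exist for the subject:

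| Subject | RZB date | APR date | Window ends |
|---|---|---|---|
| Arm 1 | 281 + 140 = 421 | none | Day 421 |
| Arm 2a | 309 + 140 = 449 | 112 + 28 = 140 | Day 140 |
| Arm 2b, not rescued | none | 365 + 28 = 393 | Day 393 |
| Rescued at Week 28 | 309 + 140 = 449 | 196 + 28 = 224 | Day 224 |
| Rescued at Week 40 | 309 + 140 = 449 | 280 + 28 = 308 | Day 308 |

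- As written, from first dose: Days 1 to 140 in Arm 2a against Days 1 to 393 in non-rescued Arm 2b; 393/140 = 2.8.
- Period B starts only: 140 − 113 = 27 days against 393 − 113 = 280 days; 280/27 = 10.4.
- Arm 2a against its own risankizumab window: 449 − 113 = 336 days, of which 449 − 140 = 309 (92%) are not counted.

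The gap in the reported percentages cannot be computed. Pre-dose medications that continue, and starts on Days 1 to 112, are counted alike in both arms.

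**2. ALL_RZB patient-years at the Period B analysis**

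Assumptions not in the documents: 110 Arm 1 and 110 Arm 2a subjects, all complete, no rescue, uniform accrual, and a cutoff at the last subject's Week 16 (Period A) or Week 52 (Period B).

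With no cutoff, Arm 1 contributes 421 − 1 = 420 days and Arm 2a 449 − 113 = 336 days per subject: 110 × (420 + 336)/365.25 = 227.7 patient-years. The cutoff plus one day falls on Day 366 for the last subject enrolled, so the largest excess per subject is 421 − 366 = 55 days (Arm 1) or 449 − 366 = 83 days (Arm 2a).

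| Accrual | Period B cutoff | No cutoff | Period A cutoff |
|---|---|---|---|
| 6 months | 219.5 | 227.7 (+3.7%) | 89.3 (−59%) |
| 9 months | 222.2 | 227.7 (+2.5%) | 116.8 (−47%) |
| 12 months | 223.6 | 227.7 (+1.8%) | 142.6 (−36%) |
| 18 months | 225.0 | 227.7 (+1.2%) | 170.9 (−24%) |

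Protocol 5.6 waives the follow-up call for subjects who start commercial drug, so some may end participation at Week 52. If half do, the no-cutoff excess falls to 2.0% (6 months) and 0.7% (18 months).

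**The case against.** The best defence of SAP 7.3 is that a programmer would apply it by period and by drug. A switched subject takes no apremilast in Period B, so the apremilast term would drop out and the problem would vanish. That is true, but 7.3 does not say it, whereas SAP 10.2.1 spells out period- and drug-specific windows for treatment-emergent events. The defence is also right about size: the tenfold ratio describes only the Period B slice. Over the window as written, the ratio is about 2.8.

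For 10.2.4, each bracket refers to a cutoff during a named primary analysis, which reads most naturally as a cap applied only at that analysis. This stands. It leaves ALL_RZB uncapped at the Period B analysis, a small effect, and leaves the final analysis at study completion untouched. A reader might infer from the label that a quarter to more than half of the exposure is lost. That requires applying the Period A cutoff at the Period B analysis, which is the less natural reading.

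A reader might also infer that alternative psoriasis treatments started after Day 140 would be missed in the Week 52 non-responder rule. The documents do not support this. SAP 8.0 defines the intercurrent events without reference to the 7.3 window, and no test or estimand uses ALL_RZB patient-years.

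**Conclusion.** Both defects stand in the current text, and both are minor.

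- **SAP 7.3:** followed exactly, the rule leaves out collected data unequally between the re-randomized arms. The dates are nominal; the ±3-day visit window moves Day 140 to between Day 137 and Day 143. The rescued-subject dates rest on the assumed apremilast stop.
- **SAP 10.2.4:** the ALL_RZB line conflicts with SAP 6.0 and with its neighbours on either reading of the bracket. The likely effect is a denominator about 1% to 4% too large at the Period B analysis, under the accrual, dropout and rescue assumptions above. The 24% to 59% shortfall applies only on the less natural reading.

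Neither point changes a primary or ranked endpoint.

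**What to change.** **SAP 7.3.** For the ITT_B_NR and ITT_B_R tables, replace the minimum with the later of the two dates that apply to the subject (last RZB dose + 140 days, last APR dose + 28 days). Arm 2a and rescued subjects then run to Day 449; single-drug subjects do not change. Flag or show separately medications started after the first rescue dose. End the ITT_A table at the first Period B dose. If the tables are made period-specific, state that Period B concomitant medications are those taken on or after the first Period B dose, including those started earlier and continuing.

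Copying the SAP 10.2.1 windows unchanged would not serve. They end at the first rescue dose (Day 197 or 281), 27 days earlier than the present rule (Day 224 or 308), and would leave post-rescue medications in no listed table, since 7.3 lists none for ITT_Res. The downside of the later date is that windows still differ by arm: 336 days (48 weeks) against 280 days (40 weeks) from Week 16 for APR/RZB and non-rescued APR/APR. Show the window length with the table.

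**SAP 10.2.4.** In the ALL_RZB line, write *the cutoff date of the analysis being performed*. The same wording in SAP 6.0 is optional and matters only if ALL_RZB is reported at the Period A analysis.

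**Cost.** SAP wording in two places (a third if 6.0 is aligned) and the matching programs, including the rescue flag. No new data are needed and no efficacy analysis changes.
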